Ocular protection: In addition to providing the ocular surface with moist, ocular protection in the forms of drops has proved advantageous. Sodium hyaluronate and disaccharides have been included in eye drops with the aim of increasing ocular protection. Sodium hyaluronate containing solutions have been demonstrated to result in improvement in dry eye in patients compared to other lubricant solutions in several studies.^{13,14} Naturally occurring disaccharides, which are a major component in Thealoz, are used with the purpose of protecting the cells of the cornea and conjunctiva as well as to give resistance to dryness. Thealoz has proved successful in clinical studies.^{15,16}

Study Description

Aims: To compare the effects of THERA°PEARL Eye Mask with the use of Blephasteam®.

Study Design

All the studies will be conducted based on written consent of the patients. Moreover, they will be performed in accordance with the tenets of the Helsinki Declaration and after approval from the Regional Ethics Committee as well as. If the patients encounter any problems during the study, they will be examined, irrespective of the planned follow-ups. The patients are free to quit the study at any time for any reason.

To answer our aim, we have, in brief, chosen the following study design:

1) THERA°PEARL Eye Mask versus treatment with Blephasteam®. In both groups, 60 patients with MGD are enrolled. We aim to make the two groups comparable as to the severity of the disease, age, and gender. The patients will be examined before the treatment and after 3 months, and 6 months. Treatment for both groups will be according to the manufacturer. All the analyses mentioned in the section *analyses* are planned to be included at every examination. Inclusion criteria: Meibomian gland dysfunction and candidate for eyelid heat therapy. Diagnosis of at least mild severity will be based upon recommendation by the diagnostic subcommittee of the International Workshop on Meibomian Gland Dysfunction, as seen in Table 1.

Ocular Surface Disease Index (OSDI)	>12
Quality or expressibility score	≤20 years old: >1 >20 years old: ≥1
Non-invasive tear film break-up time (NITBUT)	<10 s in at least one eye
Schirmer-1 test	>5 mm after 5 min in at least one eye

Exclusion criteria: Glaucoma, ocular allergy, autoimmune disease, contact lens-wear during study, current punctal plugging, pregnant/lactating, candidate for topical anti-inflammatory therapy, or cicatricial MGD.

Analyses

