Tear film osmolarity. TearLab TM Osmolarity system (TearLab, San Diego, CA) will be used. It requires a very small volume of tears (50nL), which will be collected at the inferior lateral meniscus.

Luminex. A multiplex Luminex® bead-based assay will be used to analyze ten cytokines (interleukin 1 α [IL-1 α], IL-1 β , IL-1ra, IL-4, IL-6, IL-8, IL-10, IL-13, monocyte chemoattractant protein-1 [MCP-1], and tumor necrosis factor- α [TNF- α]) and five metalloproteinases (MMPs) (MMP-1, MMP-2, MMP-7, MMP-9, and MMP-10). The Luminex bead-based assay is based on the principle of flow cytometry. The system allows us to simultaneously measure numerous analytes in a single microplate well, using very small sample volumes²⁵ while for many cytokines achieving excellent correlations to individual Enzyme-linked immunosorbent assay (ELISA).²⁶ Recently, Luminex has been used to measure the cytokine content in tear

samples collected with capillary tubes^{27,28} or Schirmer strips.²⁹ The analyses will be performed at the Department of Medical Biochemistry, Oslo University Norway. The content of cytokines and MMPs will guide us in the evaluation of the effectiveness the treatment. Moreover, it will shed light on the pathological mechanisms. As the important role of inflammation in DED has gained considerable scientific support recent years, a Luminex based approach seems pertinent in a clinical setting.

Confocal microscopy. Heidelberg Retina Tomograph with Rostock corneal module (<http://www.heidelbergengineering.com/products/hrt-glaucoma-module/cornea-module/>) is considered a state-of-the art diagnostic tool to evaluate the cornea at high magnification. In the present proposal, the density of presumed inflammatory cells in the central and peripheral cornea, subbasal nerve fibers, and epithelial wing cells will be investigated. Two independent investigators will evaluate the confocal pictures, and inter-observer variability will be measured to further assess the robustness of the method.

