Keratograph 5M. Keratograph 5M (Oculus, Germany) technology will be used to enable meibography, which is a novel *in vivo* technique that provides photographic documentation of the meibomian gland, including the ducts and acini, under specialized illumination. *In vivo* confocal microscopy has the advantage of very high resolution, but at the expense of the overview. Both detailed analyses of selected glands and an overview of the general health of all the glands in the eyelids are important to be able to decide upon the best treatment strategies.

Integrative approach. The Dry Eye WorkShop (DEWS) severity scale³⁰ will be used as it integrates the values derived from the following analyses in one single score: tear osmolarity, Schirmer tests, TBUT, corneal staining, meibomian score, conjunctival staining, and OSDI.

Data Management and Statistical Analysis Plan

All data will be stored in a special electronic medical record system built for management of dry eye disease. The extraction of the patient data from the system database will be carried out according to guidelines by the Regional Ethical Committee and the Norwegian Data Protection Agency. The dataset will be de-identified prior to any statistical analyses.

All data will be checked for normality to determine the appropriate parametric or non-parametric test. To test for differences among groups, relevant Chi square test, one-way analysis of variance (ANOVA) and Kruskal–Wallis equality- of-populations rank test will be used. Where there is difference among groups, relevant Student's t test or Wilcoxon rank sum test will be performed. Chi square test will be used to evaluate the differences in the primary and secondary outcomes between groups. Logistic regression will be used to adjust for baseline differences. Statistically significant difference is based on 0.05 level of significance. All analyses will be performed with SPSS software, version 24 (IBM Corp., NY, USA).

Missing data will be handled with last observation carried forward.

Zero-hypotheses: Blephasteam® (Spectrum Thea Pharmaceuticals LTD, Macclesfield, UK) and THERA°PEARL Eye Mask (Bausch & Lomb Inc., New York, USA) differ by a clinically relevant amount. Type I error rate of 0.05 and power (type II error rate) 0.20. There are many parameters that will be measured in the study, the primary being tear film break-up time (TFBUT).

Originality and Scientific/Clinical Value

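### A normality check on the trial's own data chooses among tests that all ignore baseline, and no usable baseline-adjusted analysis is named for measured outcomes

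*Combined protocol and SAP*

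**What the plan says.** All of this comes from one paragraph of the Data Management and Statistical Analysis Plan section, except the visit schedule and the list of measurements.

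- Choice of test: "All data will be checked for normality to determine the appropriate parametric or non-parametric test". No normality test or threshold is named. The paragraph does not say whether the check is made per outcome, arm or visit, or on raw values or changes.
- First stage: "To test for differences among groups, relevant Chi square test, one-way analysis of variance (ANOVA) and Kruskal–Wallis equality- of-populations rank test will be used".
- Second stage: "Where there is difference among groups, relevant Student's t test or Wilcoxon rank sum test will be performed".
- A separate sentence on the outcomes: "Chi square test will be used to evaluate the differences in the primary and secondary outcomes between groups".
- Baseline: "Logistic regression will be used to adjust for baseline differences".

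Study Design enrols 60 patients per group, examines them before treatment and at 3 and 6 months, and says that all the listed analyses "are planned to be included at every examination". These include OSDI, osmolarity, Schirmer, tear meniscus, confocal densities and a Luminex panel: the "bead-based assay will be used to analyze ten cytokines" plus five metalloproteinases, so 15 analytes. The primary, tear film break-up time, is also a measured time. No ANCOVA, mixed model or transformation is named, and no responder cut-off is defined for any measured outcome.

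**The concern.** Whether an outcome is compared on means or on ranks would be settled only after the trial data are in hand. Whichever branch is taken, the comparison uses follow-up values alone, although each patient's starting value is known.

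The paragraph also gives measured outcomes two incompatible instructions. One is t/ANOVA or rank tests, depending on normality. The other is chi square, which cannot be run on a concentration or a time without a cut-off.

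At stake are precision and a clear effect estimate. The aim is to say how far two devices differ, and the Luminex subsection intends the cytokine and MMP results to inform the judgement of effectiveness. Both need an estimate with an interval on a known scale, and the listed tests do not commit to one.

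**Working it through.** **Inputs from the documents.** 60 per group, two groups, alpha 0.05 (taken as two-sided), type II error 0.20 (read as 80% power).

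**Assumed inputs.** The documents give no SD, skewness, baseline correlation, effect size or dropout rate. I assume log-normal outcomes, baseline correlation r of 0.3, 0.5 or 0.7, Shapiro–Wilk at 5% in each arm as the normality check, and complete data.

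**Step 1: the plan's own figure.** The 60 per group cannot be reproduced without an effect size, SD or margin. The effect it implies for a simple two-mean comparison is d = (1.960 + 0.842) × √(2/60) = 0.51 SD.

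**Step 2: what baseline adjustment is worth.** Adjusting for baseline multiplies the residual variance by 1 − r², so power = Φ(d/√(1 − r²) × √(60/2) − 1.96). For a shift of d = 0.4 log-SD:

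| Analysis | Calculation | Power by formula | Power by simulation |
|---|---|---|---|
| Unadjusted log-scale t test | Φ(0.400 × 5.477 − 1.96) | 59% | 57% to 61% |
| Plan's rule (t or Wilcoxon after the check) | none | none | 56% to 60% |
| Log ANCOVA, r = 0.3 | Φ(0.419 × 5.477 − 1.96) | 63% | 61% to 64% |
| Log ANCOVA, r = 0.5 | Φ(0.462 × 5.477 − 1.96) | 72% | 70% to 72% |
| Log ANCOVA, r = 0.7 | Φ(0.560 × 5.477 − 1.96) | 87% | 84% to 87% |

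At the implied effect of 0.51 SD, the same formula moves power from 80% to 84%, 90% and 98%. Equivalently, adjustment would reach the unadjusted precision with 60 × (1 − r²), or about 55, 45 and 31 per arm. Confidence intervals shrink by the factor √(1 − r²) = 0.95, 0.87 and 0.71, whichever hypothesis is being tested.

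**Step 3: what the normality rule itself costs.** The fair comparison is the rule against the unadjusted log-scale t test, since neither uses baseline: 56% to 60% against 57% to 61%. The difference is 0 to about 3 points across settings. With no true difference, the rule rejected in 4.2% to 5.8% of simulated trials, so there is no material inflation.

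**Step 4: can one outcome get different tests at 3 and 6 months?** Only if the check is made visit by visit, which the plan does not say. On that assumption, with correlation 0.5 between visits:

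| Distribution | Visits get different tests |
|---|---|
| Normal | 17% to 18% |
| Log-SD 0.15 | about 46% |
| Log-SD 0.3 | about 20% |
| Log-SD 0.5 or more | about 0% |

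At log-SD 0.5 or more the rank test is chosen over 99% of the time, so strongly skewed outcomes are treated consistently.

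**Step 5: does the scale of the replacement matter?** Yes. At log-SD 0.8 to 1.0 and r of 0.3 to 0.5, ANCOVA on the original scale had 42% to 54% power, against 56% to 57% for the plan's rule. An adjusted model on a badly chosen scale can do worse than what it replaces.

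**The case against.** The case for leaving the plan alone has real substance.

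- **Pre-testing does little harm here.** This stands. A reader might infer that choosing the test from the data inflates false positives. The simulations do not show it.
- **The rank test is not the cause of the power loss.** This also stands. It is tempting to say that skewed outcomes lose substantial power because they are sent to Wilcoxon. But Student's t and ANOVA omit baseline just as completely, and the unadjusted log-scale t test gains almost nothing over the rule. The loss comes from the missing adjustment, in both branches.
- **Switching tests between visits is not established.** A reader might take it as planned. The documents give no unit for the check. Even if it is made per visit, the problem is confined to near-normal or mildly skewed outcomes.
- **The plan does name a baseline adjustment and an outcome test.** This stands only in part. Logistic regression and chi square are named, so it would be wrong to say that baseline is ignored altogether or that normality alone governs every outcome. Neither method can be applied to a measured value without a cut-off, and none is given. For these outcomes the t/rank branch is the only workable instruction, and it contradicts the chi-square sentence.
- **The gain rests on assumed correlations.** True. At r = 0.3 it is only about 5 points. It does not disappear anywhere in the range shown, provided the scale is suitable.

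**Conclusion.** The point holds as one about precision and prespecification. For measured outcomes the plan lets trial data choose among tests that all omit baseline, names no adjustment that can be used, and contradicts itself by also assigning chi square. The normality rule alone costs at most about 3 points of power and leaves type I error near 5%. The missing adjustment costs roughly 5, 13 and 28 points at baseline correlations of 0.3, 0.5 and 0.7 (for example 59%, 59% and 59% unadjusted against 63%, 72% and 87% by formula).

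These sizes assume 60 complete patients per arm, a 0.4 log-SD shift and log-normal outcomes analysed on the log scale. None of the distributional inputs is in the documents. The documents do not support calling the results invalid, or saying that tests will in fact differ between visits.

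**What to change.** In the Data Management and Statistical Analysis Plan section:

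1. Replace the normality rule for measured secondary outcomes with one linear model per outcome, containing device and that outcome's own baseline value. Use the same model at 3 and 6 months. Report a difference, or on the log scale a ratio of geometric means, with a 95% confidence interval.
2. Fix the scale of each outcome before any comparison by group. Use the log scale for the 15 Luminex analytes. For OSDI, osmolarity, Schirmer, meniscus and confocal densities, choose the scale from existing clinic data or from blinded pooled baseline data, not the original scale by default (Step 5 shows why).
3. Confine chi square and logistic regression to outcomes that are categorical, so that the sentences no longer conflict. The primary is also a measured time, so its own analysis must be stated explicitly when the chi-square sentence is reworded.
4. Keep a rank test as a sensitivity analysis.

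The cost is a little SAP drafting and analysis work. No patients, visits or measurements are added, because baseline values are already planned, and the named software fits the model.

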McMonnies Dry Eye Questionnaire. The McMonnies Dry Eye Questionnaire has been considered to be the "gold standard" for examining dry eye symptoms. The validity of the theory behind the questions and the questionnaire's usefulness in clinical settings has been demonstrated in numerous research articles.¹⁷ In addition, Ocular Surface Disease Index [OSDI] will be applied.¹⁸

Slit lamp examination. The cornea will be evaluated for the presence of active inflammation or structural change. The iris and anterior chamber will be assessed for sign of inflammation, whereas the eyelids will be evaluated for sign of Meibomian gland dysfunction with grading of the quality, expressibility, and volume of gland secretion, according to the Bron/Foulks scoring system.¹⁹

Tear film quantity and quality. RTVue (Optovue Inc, Fremont, CA) (http://www.optovue.com/wp-content/uploads/RTVue-Single-Sheet-Brochure_RevF.pdf) is the most comprehensive High Definition Ocular Coherence Tomography (OCT) system available today.²⁰ The Cornea Anterior Module unit for the RTVue system provides a rapid, non-contact, non-invasive method for producing high-quality images (5 micrometer resolution) that enable measurements of the tear meniscus. The overall tear volume can quite well be predicted by measuring the tear meniscus size^{21,22} as the meniscus contains 75% to 90% of the tear volume²³. Its size is related to the tear secretion rate²³ and the tear stability.²⁴ In addition, the Schirmer test, a traditional tear production measurement, will be applied with and without anesthesia. TBUT (fluorescein break-up time) will be used to test the quality of the tear film. TBUT will be measured after instilling 5 uL of a 2% sodium fluorescein solution. The average of three consecutive break-up times manually determined with a stopwatch will be calculated. Corneal staining will be evaluated under cobalt blue illumination 2.5 to 3.0 minutes after fluorescein instillation. The staining amplitude will be measured according to the National Eye Institute (NEI)/Industry Workshop scale.² Likewise, conjunctival staining will be investigated 2.5 to 3.0 minutes after 10 uL of a 1% sodium lissamine green dye is instilled. Conjunctival staining amplitude will be assessed in accordance with the NEI/Industry Workshop scale.²

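### The plan assigns a chi-square test to a primary outcome measured in seconds, gives no cut-off, and conflicts with its own normality-based rule for choosing tests

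*Combined protocol and SAP*

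**What the plan says.** The Data Management and Statistical Analysis Plan names TFBUT as the primary parameter. Under Analyses, Tear film quantity and quality, fluorescein break-up time is obtained as follows: "The average of three consecutive break-up times manually determined with a stopwatch will be calculated". The other break-up measure, NITBUT in Table 1 of Study Design, is also expressed in seconds. TFBUT is therefore a time whichever of the two is meant.

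The statistical paragraph makes three statements that bear on how TFBUT is analysed:

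- A general rule: "All data will be checked for normality to determine the appropriate parametric or non-parametric test". It is followed by a list of chi-square, one-way ANOVA and Kruskal-Wallis tests. Where those show a difference, a further Student's "t test or Wilcoxon rank sum test will be performed". None of these is tied to a named outcome.
- An assignment to outcomes: "Chi square test will be used to evaluate the differences in the primary and secondary outcomes between groups".
- Adjustment: "Logistic regression will be used to adjust for baseline differences".

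No responder definition or outcome cut-off appears. The only break-up-time limit is "<10 s in at least one eye", an entry criterion for NITBUT.

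**The concern.** A chi-square test compares proportions, so TFBUT would first have to be cut into categories, and the plan does not say where. The normality rule points the other way, to a comparison of seconds by a parametric or rank test. A reader cannot tell which test, on which scale, at which cut-off, produces the main p-value, and the analyst could settle this after seeing the data.

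Two things are at stake. Any freedom to choose the test or the cut-off after seeing the data raises the false-positive rate above the nominal 5%. If the chi-square and logistic sentences govern, information in the measured times is discarded. The adjusted result would then be an odds ratio at an unspecified threshold, not a difference in seconds that a clinician can read.

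**Working it through.** **What the plan's own figures allow.** The stated inputs are 60 patients per group, significance level 0.05 and type II error 0.20. No effect size, SD, responder rate or cut-off is given, so the sample size cannot be reproduced. A two-sided test is assumed because sidedness is not stated. Solving backwards:

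- Normal approximation: (1.960 + 0.842) × √(2/60) = 0.511 SD.
- Non-central t, 118 degrees of freedom: 0.516 SD for 80% power. This value is used below.

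**False positives when the cut-off is free.** These are simulations with 60 per group, no true difference and 20,000 trials, taking the largest chi-square over cuts defined by pooled ranks. Because only ranks are used, the rates hold for any continuous distribution.

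| Cuts available | Uncorrected | Continuity-corrected |
|---|---|---|
| One fixed median cut | 4.5% | – |
| Best of three quartile cuts | 13% | 7% |
| Best of nine decile cuts | 22% | 18% |
| Any cut, 10th to 90th percentile | 42–43% | 29–30% |

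**False positives from the choice of rule alone.** Under the same null with a normal outcome, reporting whichever of the t-test and a median-split chi-square is significant gives about 7.5%. Adding the Wilcoxon test gives about 7.9%.

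**Power, unadjusted, normal outcome, shift 0.516 SD.** For a cut midway between the group means, the proportions above it are Φ(−0.258) = 0.398 and Φ(0.258) = 0.602, a difference of 0.203. The pooled standard error is √(2 × 0.5 × 0.5/60) = 0.0913. The unpooled one is √(2 × 0.398 × 0.602/60) = 0.0894. Approximate power is Φ[(0.203 − 1.960 × 0.0913)/0.0894] = Φ(0.28), or 61%. Simulation of the actual test gives:

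- t-test: 80%
- chi-square, midway cut: 62% (55% corrected)
- chi-square, cut 1 SD above the control mean: 53% (43% corrected)

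**Power with baseline adjustment.** ANCOVA multiplies the residual SD by √(1 − ρ²), where ρ is an assumed correlation of TFBUT with its baseline value; the documents give none. At ρ = 0.5, for example, 0.516/√0.75 = 0.595 residual SD.

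| ρ | Logistic regression, midway cut | ANCOVA in seconds |
|---|---|---|
| 0.3 | 63% | 83–84% |
| 0.5 | 69% | 89–90% |
| 0.7 | 77% | 97–98% |

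The ANCOVA ranges span simulation and formula.

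**Dependence on the distribution.** For log-normal data with log-scale SD 0.4 to 0.8, chi-square has 63%, a t-test on log seconds 80%, and a t-test on raw seconds 77% falling to 68%. For heavy-tailed (Laplace) data the order reverses: chi-square 93%, Wilcoxon 91%, t-test 80%.

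**The case against.** The strongest defence is that the paragraph is a generic list from which the relevant test is picked by variable type. The normality check then covers TFBUT, and the chi-square sentence is loose drafting meant for categorical outcomes. That may be the intention. But the sentence names the primary outcome expressly, the only primary outcome is a time, and no sentence assigns a t or Wilcoxon test to it. That both readings are possible is itself the problem. Even the kinder reading contains no adjusted analysis in seconds.

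Several caveats stand:

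- The 43% is a ceiling. It requires trying every cut in the range and reporting the best, and nothing suggests the investigators intend this. The choice between rules alone costs far less, about 7.5%.
- The power figures rest on an assumed effect and distribution, and they reverse for heavy tails.
- The ANCOVA figures assume groups with equal expected baselines. The available text says only that comparability on severity, age and gender is aimed for.
- The null hypothesis is worded as the devices differing by a relevant amount, which reads as an equivalence null, but no margin is given. All the rates above are for tests of difference. Every test the plan lists is of that kind, so they describe the planned analysis, but equivalence power cannot be computed.
- Baseline adjustment is already planned, and the logistic model could include baseline TFBUT. What is missing is an adjusted effect in seconds.

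**Conclusion.** The concern holds, and the plan is wrong as written on the decisive test for its primary outcome. Chi-square is assigned to a continuous measure with no cut-off, a conflicting rule stands in the same paragraph, and nothing says which prevails. This must be fixed before the data are analysed.

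The false-positive rate ranges from about 7.5% for a choice between two tests to 13–22% for a modest search over cut-offs, with 43% as the extreme. The cut-off rates need only a continuous outcome; the 7.5% assumes normality. The power loss, roughly 80% to 62% or less, is an illustration for normal data and is similar for log-normal data analysed on the log scale. It is not a property of every distribution, and the conclusion does not depend on it.

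**What to change.** Replace the chi-square and logistic sentences, as they apply to TFBUT, with one primary analysis. Suggested wording: *The primary analysis is ANCOVA of TFBUT in seconds at [one named time point, for example 6 months] on treatment group, with baseline TFBUT as covariate (and age and gender if wanted), reporting the adjusted mean difference with its 95% confidence interval.*

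In the same edit:

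- State whether TFBUT means the fluorescein measure or NITBUT, and which eye or eye average is analysed.
- Fix the rule for skewed data in advance: either log seconds reported as a ratio, or a rank-based ANCOVA.
- Do not use the DEWS severity score as a covariate. It combines "in one single score: tear osmolarity, Schirmer tests, TBUT, corneal staining, meibomian score, conjunctival staining, and OSDI", so it already contains break-up time.
- Keep chi-square and logistic regression for outcomes that are categorical. If a TFBUT responder analysis is wanted, make it secondary and write its cut-off into the plan now.
- Drop the step from ANOVA to t-test, which is redundant with two groups.

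The confidence interval is useful whether the question is difference or equivalence, but an equivalence claim would also need a stated margin.

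The cost is SAP wording and the decisions it records. All listed analyses are already planned before treatment and at 3 and 6 months, so no patients, visits or procedures are added.

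### The plan names Chi square for all outcomes while also naming rank tests. If Chi square is used on the ordered grades, their order is ignored and power is lost

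*Combined protocol and SAP*

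**What the plan says.** In Data Management and Statistical Analysis Plan, one sentence links a test to outcomes by their role: "Chi square test will be used to evaluate the differences in the primary and secondary outcomes between groups". It names no trend version, ordinal model or cut-point.

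The same paragraph also contains:
- a rule for choosing tests: "All data will be checked for normality to determine the appropriate parametric or non-parametric test";
- a list for comparing groups: "relevant Chi square test, one-way analysis of variance (ANOVA) and Kruskal–Wallis equality- of-populations rank test will be used";
- a follow-up step: "Where there is difference among groups, relevant Student's t test or Wilcoxon rank sum test will be performed";
- logistic regression for baseline differences;
- the threshold: "Statistically significant difference is based on 0.05 level of significance".

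The ordered outcomes are described elsewhere. Under Analyses, the slit lamp paragraph calls for "grading of the quality, expressibility, and volume of gland secretion, according to the Bron/Foulks scoring system". The tear film paragraph grades corneal staining on a named scale and adds that "Conjunctival staining amplitude will be assessed in accordance with the NEI/Industry Workshop scale". The paragraph on the integrative approach adds the DEWS severity scale. The inclusion table under Study Design sets thresholds on the meibum score, so the plan itself treats that score as ordered.

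Break-up time is named as primary among many parameters. No outcome is labelled secondary, and no number of grades is given for any scale.

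**The concern.** A Chi square test on a grade-by-group table treats the grades as unordered labels. A consistent move toward better grades counts no more than an irregular scatter of the same size, and the degrees of freedom rise with the number of grades. A rank test or an ordinal model puts its sensitivity into the single direction of better versus worse.

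The section Recent advances describes heating as melting the secretion and unblocking the glands. An effect of that kind runs in one direction, and the meibum grades are among the outcomes that would record it. The plan's hypothesis is worded as the two devices differing by a relevant amount, so a non-significant result could easily be read as showing that they are alike. Lost power on the grades makes that misreading easier.

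The follow-up wording adds to the problem. If Chi square is the first step and Wilcoxon follows only where a difference is found, a shift that Chi square misses never reaches the test that could detect it.

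This point is confined to the ordered grades. It does not deal with break-up time, which is measured in seconds.

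**Working it through.** **Inputs from the documents.** 60 patients per group (Study Design); level 0.05; "Type I error rate of 0.05 and power (type II error rate) 0.20", where 0.20 is read as the type II error, so power is 0.80. Two-sided testing is assumed.

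**Inputs not in the documents, therefore assumed.** The number of grades, their distribution and the effect size. Ranges are shown below.

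**1. The plan's own figure.** No effect size, SD or rate is given, so 60 per group cannot be reproduced. It can only be solved backwards for a comparison of two means: d = (1.960 + 0.842) × √(2/60) = 2.802 × 0.1826 = 0.51 SD. This says nothing about the graded outcomes.

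**2. Analytic check.** Suppose an ordered test on 1 degree of freedom has 80% power. Its noncentrality is (1.960 + 0.842)² ≈ 7.85. Give the unordered test the same noncentrality on k − 1 degrees of freedom for k grades, and compute P[χ²(k − 1, 7.85) > 95% critical value]:

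| Grades k | Power lost (points) | Power left (80% − loss) |
|---|---|---|
| 2 | 0 | 80% |
| 3 | 9.1 | 70.9% |
| 4 | 15.5 | 64.5% |
| 5 | 20.5 | 59.5% |
| 7 | 27.9 | 52.1% |

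With ordered-test power of 50% to 70%, the loss is 15.5 to 16.9 points for 4 grades and 19.2 to 21.8 for 5. At 90% it is 11.6 and 16.0.

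**3. Simulation.** 10,000 trials per setting, 60 per group. The shift is logit(cumulative probability, group B) = logit(cumulative probability, group A) + ln(OR). The tests are:
- Pearson X² = Σ(O − E)²/E on (occupied grades − 1) degrees of freedom;
- Wilcoxon z = (W − n(N + 1)/2)/√V, with V = (n²/12)[(N + 1) − Σ(t³ − t)/(N(N − 1))], n = 60, N = 120 and t the number of patients tied at each grade.

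Each cell gives the rejection rate in %, Chi square / Wilcoxon.

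| Grades in group A | OR 1 | OR 1.8 | OR 2.2 | OR 2.5 | OR 3.0 |
|---|---|---|---|---|---|
| 2, equal | 5.4 / 5.4 | 35.8 / 35.8 | 55.3 / 55.2 | 68.1 / 67.8 | 82.1 / 81.8 |
| 3, equal | 5.0 / 4.7 | 31.5 / 40.4 | 53.8 / 64.7 | 66.2 / 76.1 | 82.7 / 89.3 |
| 4, equal | 5.2 / 5.2 | 28.6 / 42.1 | 48.0 / 65.8 | 62.1 / 79.1 | 79.4 / 90.8 |
| 4: 10/40/35/15% | 5.0 / 4.9 | 26.7 / 40.4 | 46.4 / 63.7 | 59.0 / 76.6 | 76.5 / 89.3 |
| 4: 40/35/20/5% | 4.8 / 5.2 | 26.1 / 40.1 | 44.4 / 62.4 | 56.4 / 74.2 | 73.3 / 86.7 |
| 5, equal | 5.1 / 5.2 | 26.2 / 43.2 | 44.9 / 66.7 | 58.6 / 79.5 | 76.1 / 91.3 |
| 5: 10/25/30/25/10% | 4.7 / 5.1 | 24.8 / 42.9 | 44.0 / 67.2 | 57.3 / 79.4 | 74.7 / 91.2 |
| 7, equal | 4.7 / 4.8 | 21.2 / 44.4 | 38.4 / 69.0 | 52.0 / 80.7 | 69.4 / 92.1 |

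For odds ratios 1.8 to 3.0 the loss is:
- 3 grades: 7 to 11 points;
- 4 grades: 11 to 18;
- 5 grades: 15 to 23;
- 7 grades: 23 to 31.

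A finely summed score with 16 levels would lose 33 to 51 points.

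**4. Grades split at the median.** At odds ratio 2.5, Chi square on the two halves has about 68% power, against 79% for Wilcoxon on four equal grades: a loss of about 11 points.

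**5. Sparse grades.** A grade held by 5% of patients has an expected count of 0.05 × 60 = 3 per group. In the 40/35/20/5% setting, some expected count fell below 5 in more than 90% of simulated trials. Type I error still stayed near 5%.

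**6. Differences that are not a shift.** With 10/40/40/10% against 25/25/25/25%, Chi square had 85% power and Wilcoxon 6%.

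**The case against.** **Rank tests are already in the plan.** This is the strongest objection, and much of it stands. The paragraph has a normality rule and names Kruskal–Wallis and Wilcoxon, both of which use the order of the grades. With two groups they give the same p-value, so if either were applied directly to the grades nothing would be lost. A reader might infer that Chi square is the only test assigned to the graded outcomes, but the text does not support that. What it supports is that the sentence specific to outcomes says Chi square, the rank tests are named without being tied to any outcome, and Wilcoxon is conditional on a difference already found. The conflict leaves the choice open until the data are seen.

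**The plan may intend yes/no outcomes.** Chi square followed by logistic regression is a coherent pair for responder outcomes. In that case the argument about degrees of freedom falls away. But no cut-point is stated, and splitting grades still costs about 11 points in the example above. For an outcome that truly has two categories there is no loss.

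**The size is not a document figure.** Correct. The documents give no number of grades, distribution or effect, so no single loss can be stated for meibum, staining and DEWS together.

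**Other inferences to avoid.** A reader might conclude that a real shift would probably be missed. With 4 or 5 grades and odds ratio 2.5, Chi square still detects it in 56% to 62% of trials. At odds ratio 1.8, Wilcoxon itself detects only 40% to 43%. Nor do the simulations show false positives to be a problem. Calling gland grade the most direct measure of the treatment would be a judgement: Recent advances gives the principal effect of the goggles as the thickness and quality of the lipid layer.

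**Conclusion.** The concern holds in a limited, conditional form. The paragraph conflicts with itself and assigns no test to the ordered grades. If its Chi square sentence is followed on the full grades, the order is ignored and a one-directional shift is more likely to be missed. At 60 per group the cost is roughly 11 to 23 points of power, assuming 4 or 5 grades and a constant odds ratio of 1.8 to 3.0. It would be 7 to 11 points with 3 grades and 23 to 31 with 7. This is a loss of power only. It is worth correcting because the correction is cheap, but it does not by itself undermine the trial. The documents do not establish that these outcomes are the secondary ones, although that is the natural reading.

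**What to change.** Replace the Chi square sentence with wording such as:

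> Outcomes recorded as ordered grades are compared by proportional-odds regression with the baseline grade as covariate, with the Wilcoxon rank sum test as the check, applied directly and not conditional on an earlier test. Chi square is kept for unordered or yes/no outcomes.

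The plan should also list the secondary outcomes and the number of grades in each scale, so that the rule can be applied without further choices.

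The cost is one sentence and a short list. SPSS 24 can run both methods, Wilcoxon is already named, and the baseline grade is planned at the first examination. There is a real trade-off: the new rule has little sensitivity to a difference in spread that does not run along the scale (85% for Chi square against 6% for Wilcoxon in the example above). The power figures are for Wilcoxon; the baseline-adjusted model was not simulated, so no gain is claimed for the adjustment.
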